11.3 INTERIM ANALYIS FOR FUTILITY

When at least 50% of the Low Risk subjects have reached the 3 year time point, an interim analysis will be performed for the primary efficacy hypothesis to determine if it is futile to continue with study follow-up through 5 years. The primary efficacy study objective is to establish with 95% confidence that the 5 year bDFS rate is >93% (the OPC). For the interim analysis the 3 year bDFS rate will be used along with the same OPC of 93%.

11.3 1. Methodology:

The determination of 3 year bDFS will be made for all subjects with sufficient data through 3 years. Next, the probability of meeting the efficacy object at 3 years will be determined using simulation. Results for the subjects w/o sufficient data through 3 years will be simulated using a binomial distribution. The assumed probability of success (i.e. bDFS) will be set at the rate that was observed for the subjects w/ 3 year data. The simulation will be run 1,000 times resulting in 1,000 complete datasets. The lower confidence interval limit for 3 year bDFS rate will be calculated, using the Wilson method, for each dataset, and probability of success will be the proportion of datasets where the lower confidence limit is below 93%.

11.3.2.Rule:

If the probability of having a successful study is less than found to be less than 20% then it will be considered futile to continue with follow-up through 5 years.

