- 11.2.2 PRIMARY EFFICACY OBJECTIVE: For the low-risk cohort, the study is powered to compare 5-year bDFS rates observed with CyberKnife to 5-year bDFS rates reported with dose-escalated external beam RT. In Beaumont's monotherapy HDR series treating LR patients, 5-yr ASTRO bDFS was 98%; in Demanes' series of 75% LR and 25% IR, this was 96%. We would expect Phoenix outcomes to be slightly higher than ASTRO outcomes at 5 years. Since CK delivers doses similar to HDR monotherapy, a conservative estimate of the success rate for CK is 97.5% for LR patients. In LR patients, prospective studies from Memorial Sloan Kettering⁷⁶ (203 patients, 81Gy) and MD Anderson⁷⁷ (32 patients, 78Gy) demonstrated 5-vr bDFS (Phoenix definition) of 92% and 93%, respectively. Thames' 9-institution review of 231 dose-escalated (70-76Gy) LR patients reported 94% 5-yr Phoenix bDFS. Thus, an objective performance criteria (OPC) for lowrisk patients treated with dose-escalated external beam RT is 93% 5-yr bDFS. Assuming the CK success rate is 97.5%, to test superiority of CK against this OPC with 80% power at the 1-sided 5% significance level will require 150 patients. Increasing the sample size by 1/(0.92*0.92) for ineligible/lack-of-data cases yields 177.22; the required sample size for low-risk patients is 178 patients.
- 11.2.3 TOTAL AND RELATIVE ENROLLMENT OF RISK GROUPS: Per sections 11.2.1 11.2.2, enrollment of 178 low-risk patients are required to compare the 5-year bDFS rate observed with CyberKnife to the 5-year OPC rate, and 120 intermediate risk patients are required to establish acceptable toxicity for each risk cohort. CaPSURE data showed a ratio of low to intermediate risk patients, using D'Amico's definition⁷⁸, of 46.8%:37.2%. This CK protocol excludes intermediate risk patients with both PSA 10-20ng/ml and Gleason 7 histology. Based on proportions of patients in these subgroups reported in Partin's⁷⁹ study, this would exclude 12% of intermediate risk patients. Combining these proportions, we would expect a ratio of low to intermediate risk patients of 1.43: 1. Thus we would expect 172 low-risk patients enrolled by the time 120 intermediate risk patients have been enrolled. Each cohort will be closed to accrual once requisite enrollment is achieved: 178 low-risk patients, and 120 intermediate risk (298 total patients)

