- 11.2.4 ACCRUAL RATE: the initial three months while institutions are obtaining IRB approval, therefore we do not expect to meet the targeted monthly accrual rate until after the first three months. The estimated accrual rate is 2.5 patients per study site per month. Expectations of 10 treating study sites assume an accrual period of approximately 11 months, or 14 month total
- 11.2.5 INTERIM ADJUSTEMENT IN ENROLLMENT: Interim analysis of the first 200 enrolled patients showed that 13 were actually ineligible because they were taking finasteride or dutasteride. Enrollment will thus be increased by 13 patients. Exclusion of patients on 5-alpha reductase inhibitors is clarified in section 5.12. We recognize that LHRH agonist/antagonist (e.g. leuprolide, goserelin, triptorelin, degarelix), hormone (e.g. DES), or peripheral blocker (e.g. flutamide, bicalutamide, nilutamide) administration given more than two months before enrollment may impact efficacy. Thus sample size (section 11.2) will be increased to insure enrollment is sufficient to achieve study objectives for the subgroup of patients naïve to such therapy. Interim analysis of the first 200 enrolled patients showed

 \Box

four had received LHRH agonists or peripheral hormone blockers. We could expect four more such patients to be enrolled through completion of the study. Thus enrollment should be increased by an additional eight patients, or 21 patients total. Applying the proportion of low to intermediate risk patients described in section 11.2.3, total enrollment will be increased to 129 intermediate-risk, and 190 low-risk (319 patient total). If subsequent interim evaluations show the estimated proportion of ineligible/lack-of-data cases is inaccurate, required enrollment will be accordingly adjusted.

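### The futility simulation in Section 11.3.1 ignores follow-up already observed in low-risk men not yet at 3 years, so the probability compared with 20% is misstated

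*Combined protocol and SAP*

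**What the plan says.** Section 11.3 plans a futility look once at least half of the low-risk men have reached 3 years. It applies the 93% objective performance criterion, set for 5 years in Section 11.2.2 ("treated with dose-escalated external beam RT is 93% 5-yr bDFS"), to the 3-year bDFS rate.

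Section 11.3.1 determines 3-year status for men with *sufficient data* through 3 years, a term that is not defined. For the others: "Results for the subjects w/o sufficient data through 3 years will be simulated using a binomial distribution". The simulation probability is fixed by the next sentence: "The assumed probability of success (i.e. bDFS) will be set at the rate that was observed for the subjects w/ 3 year data". A Wilson lower limit is computed for each of 1,000 completed datasets. Under Section 11.3.2, follow-up to 5 years is considered futile if the resulting probability of success is below 20%.

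Three other sections show what would be known at that point:

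- Section 11.2.4 expects accrual to take "approximately 11 months, or 14 month total".
- Section 9.1.4 schedules PSA at 3, 6, 12, 18 and 24 months, then every 6 months to year 5.
- Section 9.4.1.1 fixes a Phoenix failure when it occurs, without backdating.

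Section 11.4.2.3 plans Kaplan-Meier curves for the Section 9.4 outcomes, but the futility rule does not use them.

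**The concern.** The men to be simulated are not blank records. Under the planned accrual most have completed well over two years, and any failure among them is already dated. Drawing each of them afresh at a full 3-year risk ignores this. An event-free man at month 34 is given 36 months of risk again.

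A man who failed at month 20 has no stated place. The text supports three readings:

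- **A.** His status is known, so he joins the observed group. His event-free peers do not, which inflates the failure rate used for simulation.
- **B.** Only men who reached 36 months are observed. His failure is set aside and redrawn.
- **C.** His failure is kept, the rate comes from men at 3 years only, and the event-free men are redrawn at that full rate.

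None of the three uses event-free time. The result is the only number compared with 20%. If the rule ends follow-up, the 5-year efficacy endpoint is not observed. An undefined term also leaves the choice of reading open until the data are in hand.

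**Working it through.** **The plan's own figure.** Section 11.2.2 assumes "a conservative estimate of the success rate for CK is 97.5% for LR patients" and states: "to test superiority of CK against this OPC with 80% power at the 1-sided 5% significance level will require 150 patients". With p0 = 0.93 and p1 = 0.975:

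n = [(1.645·√(0.93·0.07) + 0.842·√(0.975·0.025)) / 0.045]² = 149.97, so 150. Then 150/0.92² = 177.22, so 178.

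Both reproduce. The plan gives no operating characteristic for the futility rule.

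**Inputs.** 190 low-risk men (Section 11.2.5), 95 of them at 3 years. Assumed: uniform 14-month accrual, constant hazard, no loss to follow-up. The 95th man enters at month 7, so the look falls at month 43 and the last man has 43 − 14 = 29 months. Pending men therefore have 29 to 36 months, mean 32.5, with 3.5 remaining.

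**Success limit.** Section 11.3.1 counts a lower limit below 93% as success, the opposite of Section 11.4.1.2. I read it as not below 93%. By the Section 11.4.1.2 formula with n = 190:

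- 7 failures: L = (366 + 2.706 − 1.645·√(2.706 + 26.97)) / (2·192.706) = 93.3%.
- 8 failures: L = 92.7%.

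So at most 7 failures are allowed.

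**A case where all readings agree.** There are 5 failures among the 95 men at 3 years and none among the other 95.

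- As written, A, B and C alike: P(Bin(95, 5/95) ≤ 2) = 0.118, below 20%, so futile.
- Using observed follow-up: hazard ≈ 5/(95·36 + 95·32.5) = 0.00077 per month. Expected further failures = 95·3.5·0.00077 = 0.26. Poisson P(≤ 2) = 0.998.
- Counting event-free time only to the last scheduled PSA: men at 29–30 months were last measured at 24, the rest at 30. Mean remaining time = (1·12 + 6·6)/7 = 6.9 months. Hazard = 5/(95·36 + 95·29.1) = 0.00081, expected failures 0.53, P(≤ 2) = 0.98.

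**A case where the reading decides.** There are 3 failures in each half, so at most 1 more is allowed.

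| Method | Calculation | Probability |
|---|---|---|
| A | P(Bin(92, 6/98) ≤ 1) | 0.021 |
| B | P(Bin(95, 3/95) ≤ 4) | 0.82 |
| C | P(Bin(92, 3/95) ≤ 1) | 0.21 |
| Conditional on follow-up | expected 0.30 more, P(≤ 1) | 0.96 |

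**A case where B contradicts the data.** With 1 failure among men at 3 years and 7 known in the rest, P(Bin(95, 1/95) ≤ 6) = 0.9999. Yet 8 failures already exceed the limit.

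**How often futility is declared (simulated trials).**

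| True 3-year bDFS | A | C | B | Conditional |
|---|---|---|---|---|
| 98.5% (0.985^(5/3) = 97.5% at 5 years) | 14–15% | 4% | 1.7% | 0.8% |
| 97.5% (0.975^(5/3) = 95.9% at 5 years) | 48% | 23% | 10% | 9% |

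At a true 97.5%, about 89% of trials meet the 3-year criterion.

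**Sensitivity at 97.5%.** With pending follow-up of 2.5 to 3 years, the decision differs from the conditional one in 40% of trials under A, 13% under C and 10% under B. With 150 men (limit 5 failures), or pending follow-up widened to 1.5–3 years, the ranges are 31–34%, 12–18% and 8–11%.

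**The case against.** Four points on the other side carry weight.

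**Known failures need not be mishandled.** A reader might infer that the text must either over-weight or discard them. It does not: reading C does neither and fits the wording, since Section 11.3.1 uses different phrases for whose status is determined and whose rate is used. Under C the excess of futility calls is much smaller than under A. It is not nil, because event-free time is still ignored.

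**Reading B is close to correct on average.** Its futility rates are 1.7% against 0.8%, and 10% against 9%. Its fault lies in particular datasets, and the 1-and-7 split is an extreme one.

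**The 3-year criterion is not the trial's objective.** A reader might infer that these calls would wrongly end a trial that was going to succeed at 5 years. The documents do not support that. At a true 3-year rate of 97.5%, only about 47% of trials would have at most 7 failures at 5 years. In the 3-and-3 case, the same hazard carried to 5 years expects about 4.4 more failures, and P(≤ 1) = 6.6%, so stopping could be defended there. In the 5-and-0 case, remaining person-time is 90·24 + 95·27.5 = 4,772 months. That gives about 3.67 more failures and P(≤ 2) of about 0.29, which would continue. If the rule moves to 5 years, conditional projection is needed anyway, because almost no man would have complete data.

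**The figures rest on assumptions.** The 190 includes an allowance for ineligible and missing cases, and the rule permits a later look with fewer pending men. All men would also have been treated by then, so the rule governs follow-up only.

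These points limit the size and the seriousness. They do not supply the missing conditioning, and no other section does.

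**Conclusion.** The concern holds in a limited form. The written method ignores observed follow-up under every reading, so the probability set against 20% is misstated. The error can reverse the decision: 0.118 against near certainty for the 3-year criterion with 5 and 0 failures. Its frequency depends on an undefined term. At a true 97.5% the futility rate runs from about 10% (nearly right on average) to 48%, against 9%.

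This rests on 190 men, uniform 14-month accrual, constant hazard, no loss to follow-up and the corrected direction of the 93% comparison. It is a fault in how the 3-year probability is calculated, and does not show that a stop would be wrong for the 5-year objective. It should be fixed, but does not by itself invalidate the design.

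**What to change.** Rewrite Section 11.3.1 along these lines:

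- Every failure known at the interim counts as a failure.
- For each low-risk man event-free at his last PSA date t, success at the horizon is drawn with probability S(horizon)/S(t).
- S is estimated from all low-risk follow-up by one method named in advance. Kaplan-Meier and exponential estimates are not interchangeable here, because events fall on visit dates.
- Remove *sufficient data* as the dividing line, or define it.

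Apply this to whatever horizon the rule finally adopts, with a benchmark for that same horizon. In the same edit, correct the direction of the 93% comparison so that it agrees with Section 11.4.1.2. Stating the rule's futility rates under a few true bDFS values would let readers judge it.

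The cost is protocol/SAP wording, a few lines of simulation code and a modelling assumption for S. No new data are needed.

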11.4 STATISTICAL METHODS

11.4.1 PRIMARY ENPOINTS

11.4.1.1 SAFETY: The upper limit of a one-sided 95% confidence interval for the expected proportion of patients experiencing a Serious Adverse Event (SAE) is estimated by U, where

$$U = \frac{(2np + Z_{0.05}^2) + Z_{0.05}\sqrt{Z_{0.05}^2 + 4pn(1 \cdot p)}}{2(n + Z_{0.05}^2)}$$

Here "p" is the observed proportion of patients experiencing an SAE . The CyberKnife intervention will be considered to be safe if this study's result verifies that U is not above $20\%^{80}$.

11.4.1.2 EFFICACY: The lower limit of a one-sided 95% confidence interval for the expected proportion of patients experiencing biochemical disease-free survival (bDFS) is estimated by L, where

$$L = \frac{(2np + Z_{0.05}^2) \cdot Z_{0.05} \sqrt{Z_{0.05}^2 + 4pn(1 \cdot p)}}{2(n + Z_{0.05}^2)}$$

Here "p" is the observed proportion of patients experiencing bDFS in either

ACCP001.4

arm of the trial. The CyberKnife intervention will be considered to be effective if this study's result verifies that L is not below 93%.

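### The futility rule in section 11.3.1 counts failing simulated datasets as successes, so good interim results are called futile and hopeless ones continue

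*Combined protocol and SAP*

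**What the plan says.** Section 11.3 plans a futility look once at least half of the low-risk men have reached 3 years. It restates the efficacy objective as showing, with 95% confidence, a bDFS rate above the 93% OPC, and applies that OPC to the 3-year rate.

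Section 11.3.1 says "the probability of meeting the efficacy object at 3 years will be determined using simulation". Men without 3-year data are filled in from a binomial distribution at the observed rate, 1,000 times, and a Wilson lower limit is computed for each completed dataset. The text then defines the result: "probability of success will be the proportion of datasets where the lower confidence limit is below 93"%.

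Section 11.3.2 gives the decision: "If the probability of having a successful study is less than found to be less than 20% then it will be considered futile".

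The final criterion is in section 11.4.1.2. It uses "The lower limit of a one-sided 95% confidence interval for the expected proportion of patients experiencing biochemical disease-free survival", and the treatment is effective if the study's "result verifies that L is not below 93"%.

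**The concern.** A limit below 93% and a limit not below 93% are complementary events. The quantity that section 11.3.1 labels the probability of success is therefore one minus the probability of meeting the criterion in section 11.4.1.2. Compared with the 20% threshold, it declares futility when the true probability of success exceeds 80%, and continues when that probability is near zero.

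This is the plan's only efficacy stopping rule, and it is written to be run mechanically. Followed literally, it would call follow-up to 5 years futile in the situation the trial was sized to demonstrate. The primary safety objective in section 2.0 also needs five years of follow-up, so a mistaken stop could damage both primary objectives.

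A smaller gap lies beside it: section 11.3.1 names the Wilson method but not whether the limit is one- or two-sided.

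**Working it through.** **Inputs.** OPC 93%, design rate 97.5%, one-sided 5% level, 80% power, 150 evaluable and 178 enrolled low-risk men (11.2.2); 190 low-risk men after the enrolment adjustment (11.2.5); interim when at least 50% have reached 3 years, fill-in at the observed rate, 20% threshold (11.3); limit L (11.4.1.2).

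**1. The plan's own sample size reproduces.** n = [(1.645·√(0.93·0.07) + 0.842·√(0.975·0.025)) / 0.045]² = 149.97, so 150; 150/(0.92·0.92) = 177.22, so 178. At n = 150, requiring L ≥ 93% means at least 145 successes, with exact type I error 4.5% and power 82.5%. The trial is therefore sized for L at or above 93%, not below it.

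**2. Failures allowed in the complete cohort.** For N = 190 with 7 failures, p = 183/190 and z² = 2.706:

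L = [366 + 2.706 − 1.645·√(2.706 + 4·183·7/190)] / [2·(190 + 2.706)] = 359.75/385.41 = 93.3%.

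With 8 failures L = 92.7%. The maximum F is therefore 7 of 190; in the same way it is 5 of 150 and 6 of 178. With a two-sided 95% limit it is 6, 4 and 5.

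**3. The interim calculation.** With k failures among m observed men, the plan draws failures in the other N − m from Binomial(N − m, k/m). So P(L ≥ 93%) = Pr{Binomial(N − m, k/m) ≤ F − k}, and the written quantity is one minus this. I used exact probabilities in place of the 1,000 draws. For N = 190, m = 95, one-sided:

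| Failures of 95 | P(L ≥ 93%) | Written value, P(L < 93%) | As written | Corrected |
|---|---|---|---|---|
| 0 | 100% | 0% | futile | continue |
| 1 | 99.99% | 0.01% | futile | continue |
| 2 | 98.5% | 1.5% | futile | continue |
| 3 | 81.8% | 18.2% | futile | continue |
| 4 | 42.9% | 57.1% | continue | continue |
| 5 | 11.8% | 88.2% | continue | futile |
| 6 | 1.5% | 98.5% | continue | futile |
| 7 | 0.07% | 99.93% | continue | futile |
| 8 or more | 0% | 100% | continue | futile |

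The first and last rows need no assumption about hazard and are the same for a two-sided limit.

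**4. Chance of declaring futility.** Half the cohort observed, one-sided limit, k weighted by Binomial(m, 1 − S3). For a stated 5-year rate S5, a constant hazard gives S3 = S5^0.6: 97.5% becomes 98.5%, 93% becomes 95.7%, 85% becomes 90.7%.

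| | N = 150 | N = 178 | N = 190 |
|---|---|---|---|
| Futile as written, failures | 0–2 of 75 | 0–2 of 89 | 0–3 of 95 |
| Futile corrected, failures | ≥4 | ≥5 | ≥5 |
| True 5-year rate 97.5%: written / corrected | 89.6% / 2.7% | 84.9% / 1.1% | 94.4% / 1.5% |
| True 3-year rate 97.5%: written / corrected | 71.1% / 11.9% | 61.5% / 7.3% | 78.6% / 9.0% |
| True 5-year rate 93%: written / corrected | 37.5% / 39.7% | 26.4% / 33.0% | 42.0% / 38.1% |
| True 5-year rate 85%: written / corrected | 2.5% / 92.6% | 0.9% / 92.5% | 2.0% / 94.7% |

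**5. Sensitivity.** With a two-sided limit (N = 150/178/190), the written rule declares futility with probability 68.7/84.9/82.7% at a 5-year rate of 97.5% and 0.6/0.9/0.5% at 85%; the corrected rule gives 10.4/4.6/1.5% and 97.5/97.1/94.7%. If 50–90% of the cohort is observed, the written rule's figure at 97.5% runs from 85% to 98% one-sided and from 69% to 95% two-sided. The direction never changes.

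**The case against.** The strongest reply is that nobody would run the rule literally. Section 11.3 states the objective as a rate above 93%, describes the target as meeting that objective and speaks of a successful study; section 11.4.1.2 repeats the direction. An analyst who saw zero failures labelled futile would notice at once. On this view the 85–94% figures describe an execution that the surrounding text contradicts. That is fair as a forecast: the figures show what the rule does as written, not how likely someone is to follow it. It does not remove the need to correct the rule, because a prespecified rule should not depend on the analyst overriding its words after seeing the data.

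Three narrower points stand:

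- The reversal acts at the two ends. When the true simulated probability of success is between 20% and 80% (4 failures of 95, for example), both versions continue. At a true 5-year rate of 93% the two versions declare futility about equally often, though on different data.
- The text says that continuing will be considered futile. It does not order an automatic stop, and the DSMB in section 12 is advisory.
- Sidedness can be inferred from sections 11.2.2 and 11.4.1.2. At N = 190 with half observed, it makes no difference to the corrected rule's false-futility rate (1.5% either way). At N = 150 it does: 2.7% against 10.4%.

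Applying the 5-year OPC to the 3-year rate is an openly stated choice and is not contested here.

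**Conclusion.** The concern holds and must be fixed. The written success event in section 11.3.1 is the exact complement of the criterion in section 11.4.1.2, and nothing else in the document corrects it. That conclusion rests on the text alone.

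The size depends on assumptions: half the low-risk cohort observed, N of 150, 178 or 190, a one-sided 95% Wilson limit and a constant hazard. Under these, the written rule declares futility with probability 85–94% at the design rate and 0.9–2.5% at a 5-year rate of 85%, where the corrected rule gives 1.1–2.7% and 92.5–94.7%. If 97.5% is taken as the 3-year rate instead, the written rule gives 62–79% and the corrected rule 7.3–11.9%. The sample size is unaffected.

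**What to change.** In section 11.3.1, define the probability of success as the proportion of datasets whose lower limit *is not below* 93%, and state that this is the one-sided 95% Wilson limit of section 11.4.1.2. The first change restores the direction; the second settles sidedness before the simulation is programmed.

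The cost is one word and one clause. No patients, no new data and no change to the 20% threshold or the timing of the look are needed.

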2.0 OBJECTIVES

PRIMARY OBJECTIVES: The primary safety goal of this study is to estimate, in both low-risk and intermediate-risk cohorts, the rates of acute and late grade 3-5 gastrointestinal and genitourinary toxicity observed during the five years following CyberKnife SRS for prostate cancer. The primary efficacy goal is to document the rate of biochemical Disease-Free Survival (bDFS), Phoenix and ASTRO definitions, at 5 years.

SECONDARY OBJECTIVES: to measure the following in the study population: Rates of local failure, distant failure, disease-free survival, disease-specific survival, and overall survival; quality of life (QOL) in generic and organ-specific domains; work effort required in treatment planning and delivery of CyberKnife SRS.

Patients will be followed annually to 10 years, to collect additional data for descriptive analysis.

3.0 **DEVICE**

Accuray, Inc. (Sunnyvale, CA), received FDA clearance in July 1999 to provide treatment planning and image guided stereotactic radiosurgery and precision radiotherapy for lesions, tumors and conditions of the brain, base of skull and cervico-thoracic spine, head and neck using the CyberKnife. On August 10, 2001, Accuray, Inc. received 510(k) FDA clearance (510(k) number K011024) to provide treatment planning and image-guided stereotactic radiosurgery and precision radiotherapy for lesions, tumors, and conditions anywhere in the body when radiation treatment is indicated.

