11.0 STATISTICAL CONSIDERATIONS

11.1 OVERVIEW: This study's primary goal is to determine the rate of acute and late grade 3-5 gastrointestinal and genitourinary toxicity following CyberKnife treatment, and to estimate efficacy, measured as 5-year bDFS. Per RTOG/ECOG, acute toxicity will be defined as occurring within 90 days of completing treatment. Late toxicity will be defined as toxicity occurring more than 90 days after treatment. It is graded based on Common Terminology Criteria for Adverse Events (CTCAE) v3.0.(see appendix V).

11.2 SAMPLE SIZE:

11.2.1 PRIMARY SAFETY OBJECTIVE: The study is designed to test the null hypothesis that the acute and late GI/GU toxicity rate 5 years following treatment is greater than 10% versus the alternative hypothesis that the toxicity rate is less than or equal to 10%. The sample size is determined such that there is 90% probability, or power, of identifying excessive toxicity if the true toxicity rate is 20% at the one-sided 5% significance level. 101 patients must then be accrued and followed for 5 years, assuming no patients excluded or lost to follow-up. Since the treatment volume for intermediate risk patients is larger than for low-risk patients, the study will be powered to assess toxicity for both subgroups. Additional enrollment for ineligible patients, or lost to follow-up: Since performing central review of pathology prior to enrollment is impractical, some patients will be upgraded, and thus made ineligible. In RTOG 77-06, central review upgraded about 8% of Gleason 2-6 patients to Gleason 7-10⁷⁵. If we assume a similar rate of upgrading, and anticipate 8% additional ineligible/lack-of-data cases, sample size must be

- increased by 1/(0.92*0.92) = 119.33. Thus 120 patients are required to establish acceptable toxicity for each risk cohort.

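### The futility rule in 11.3 tests only low-risk bDFS, but its stated consequence is not limited to that claim and, as written, conflicts with the five-year primary toxicity objective in both cohorts

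*Combined protocol and SAP*

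**What the plan says.** The interim analysis of Section 11.3 is triggered "When at least 50% of the Low Risk subjects have reached the 3 year time point". It addresses the primary efficacy hypothesis only, using 3-year bDFS against the 93% criterion that 11.2.2 derives for low-risk patients. Its purpose is "to determine if it is futile to continue with study follow-up through 5 years". Section 11.3.2 gives the consequence: if the probability of a successful study is "less than 20% then it will be considered futile to continue with follow-up through 5 years". No cohort is named, toxicity follow-up is not exempted, and the text does not say whether the rule is binding or who applies it.

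Other sections treat five-year follow-up as fixed:

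- Section 2.0 sets a primary safety goal separate from efficacy, to "estimate, in both low-risk and intermediate-risk cohorts, the rates of acute and late grade 3-5 gastrointestinal and genitourinary toxicity observed during the five years" after treatment. It also plans annual follow-up to 10 years.
- Section 11.2.1 says that "101 patients must then be accrued and followed for 5 years", powers the study for toxicity in both risk groups, and arrives at 120 patients per cohort after inflation.
- Section 11.2.3 sizes the intermediate-risk cohort on toxicity alone.
- Section 9.1.4 schedules visits every six months to year 5 and yearly to year 10, without reference to futility.

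**The concern.** A low-risk PSA result carries no information about the five-year toxicity rate in either cohort. As worded, though, it could end the follow-up on which that rate depends. The intermediate-risk cohort is the clearest case: it has no powered efficacy hypothesis, so its main objective could be cut short by the other cohort's bDFS.

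The usual reason for a futility stop is to spare patients further exposure, and that reason is absent here because everyone has already been treated. What a stop would save is visits and data collection. What it would cost is late-toxicity information on irradiated men.

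The problem is separate from two others in 11.3: the direction in which success is counted, and the use of 3-year data for a 5-year question. It would remain if both were corrected.

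**Working it through.** **1. Does the safety design rest on five-year data in each cohort?** Inputs from 11.2.1: 10% against 20%, one-sided 5%, 90% power. One-sample normal approximation:

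n = [(1.645·√(0.10·0.90) + 1.282·√(0.20·0.80)) / 0.10]² = 101.2, against 101 stated.

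Inflation: 101/(0.92·0.92) = 119.3, hence 120. The plan's figure reproduces. For efficacy (11.2.2: 93% against 97.5%, one-sided 5%, 80% power) the same formula gives 149.97, hence 150, and 150/(0.92·0.92) = 177.2, hence 178.

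**2. Where does the interim fall?** Inputs from 11.2.4 and 11.2.5: 2.5 patients per site per month × 10 sites = 25 per month, a 3-month start-up, and 319 patients. Assumption: uniform accrual, with the same pattern in both cohorts.

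- Accrual lasts 319/25 = 12.8 months and ends at month 15.8. (Section 11.2.4 says the 10 sites "assume an accrual period of approximately 11 months, or 14 month total"; 298 patients at the same rate give 14.9 months.)
- Half the low-risk men reach 3 years at 3 + 12.8/2 + 36 = month 45.4.
- Follow-up at that point runs from 45.4 − 15.8 = 29.6 to 45.4 − 3 = 42.4 months, mean 36.
- The last man starts treatment within 90 days of registration (6.2) and finishes within 11 days (8.4.3), so by about month 19. That is about 26 months before the interim.

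Sensitivity to an accrual duration of A months: the first man has A/2 + 36 months of follow-up at the interim, so nobody exceeds 60 months if A is 48 or less. At A = 60 about 10% would have five years. All treatment precedes the interim for A up to about 65 months.

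**3. What would the safety criterion do with truncated data?** Section 11.4.1.1 requires the upper one-sided 95% Wilson limit U to be no higher than 20%. That allows at most 13 events in 101 (U = 19.3%; 14 events give 20.5%) or 16 in 120 (U = 19.3%; 17 give 20.2%). Under constant hazard, a true 5-year rate of 20% appears at a mean of 36 months as about 1 − 0.80^0.6 = 12.5%. Exact binomial probability of passing as safe when the true 5-year rate is 20%:

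| Evaluable n | Full 5 years | Truncated at the interim |
|---|---|---|
| 101 | 4.3% | about 61% |
| 120 | 3.9% | about 67% |

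**4. How likely is a stop?** Success is taken as a lower Wilson limit of at least 93%, the direction of 11.4.1.2. Half of the N low-risk men are observed and the rest are drawn at the observed rate, as 11.3.1 prescribes.

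- N = 150: at most 5 failures succeed (L = 93.3%; 6 give 92.5%). With 75 observed, the predictive probability is 0.42 at 3 failures and 0.086 at 4, so 4 or more trigger a stop.
- N = 178 (89 observed): 0.23 at 4 failures and 0.037 at 5, so 5 or more trigger a stop.
- N = 190 (95 observed): 0.43 at 4 failures and 0.12 at 5, so 5 or more trigger a stop.

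The protocol states its rates at 5 years. Under constant hazard, 93% at 5 years is 0.93^0.6 = 95.7% at 3 years, and 97.5% is 0.975^0.6 = 98.5%. Chance of a stop:

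| True 5-year bDFS | N = 150 | N = 178 | N = 190 |
|---|---|---|---|
| 93% | 40% | 33% | 38% |
| 97.5% | 2.7% | 1.1% | 1.5% |

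**The case against.** The strongest reply is that the text does not order follow-up to end. It says continuation will be considered futile, and the analysis is introduced as one for the efficacy hypothesis. It can therefore be read as closing the low-risk efficacy question only. Sections 2.0 and 9.1.4 promise follow-up without condition. Section 12 gives recommendations to continue, modify or terminate to an independent board. Section 14.7 allows five-year follow-up to be requested even after withdrawal.

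The ambiguity is real, and the broad reading should not be presented as certain. But no section states the narrow reading, and the reference to study follow-up in 11.3 points away from it. The unconditional schedule does not protect the objective. It contradicts 11.3.2 and the two are not reconciled. Section 12 never mentions the futility rule, and 14.7 concerns individual withdrawals.

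Two stronger readings are tempting and should be resisted:

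- A reader might infer that a stop would destroy the safety objective. It would not: acute toxicity and about 2.5 to 3.5 years of late toxicity would remain, and the SAE stopping table in 12.5 operates separately in each arm.
- A reader might infer that a treatment merely matching external beam would be stopped about three times in four. With N = 150 the stop chance is indeed 78%, 52% and 12% at true 3-year bDFS of 93%, 95% and 97.5%. But the criterion in 11.2.2 is a 5-year rate, so those figures answer a different question.

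**Conclusion.** The point holds as an unresolved scope and an internal conflict. Section 11.3 attaches an unrestricted consequence to a test of one cohort's efficacy, and that consequence is incompatible with Sections 2.0, 9.1.4 and 11.2.1. If the rule were applied as written, the five-year toxicity rate and its planned test would be lost in both cohorts. No man would have five-year data, against 101 evaluable men needed per cohort, and no treatment would be avoided. Applying the 20% criterion to what remained would raise the chance of passing a truly 20% toxic treatment from about 4% to about 61-67%.

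A stop is a realistic event if the treatment only meets the 93% criterion at 5 years (about 33-40%) and unlikely at the design rate of 97.5% (about 1-3%).

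The timing rests on uniform accrual at the planned rate, although the absence of five-year data holds for accrual of up to 48 months. The pass and stop probabilities assume constant hazard. The stop probabilities also assume an interim at exactly half of 150 to 190 low-risk men and the success direction of 11.4.1.2. Section 11.3.1 as printed counts a lower limit below 93% as success, which is a separate defect.

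**What to change.** Reword 11.3 and 11.3.2 along these lines: if the predictive probability is below 20%, the low-risk efficacy superiority claim is declared futile; scheduled follow-up of all patients in both cohorts continues as in Section 9, and the five-year primary toxicity analysis is carried out as planned. Remove the link between the futility result and study follow-up, and state who receives the result and whether the rule is binding.

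This takes one or two sentences and changes neither sample size nor visits. The cost is the forgone saving from closing follow-up early. The visits are already in the schedule, and under 15.1 the tests and imaging at follow-up are billed to patients' insurance.
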